### 10.2 Secondary endpoints:

- 1. Incidence of treatment-emergent adverse events (TEAE). A TEAE is defined as an adverse event with initial onset or increasing in severity after the first dose of study treatment until 30 days after last dose of study drug. TEAEs will be assessed and documented at each scheduled or unscheduled visit during the reporting period. Each TEAE will be assessed according to whether it is serious or non-serious, whether it is expected or unexpected according to the Investigator's Brochure, and whether it is related or unrelated to the study treatment. Each TEAE will be assigned a grade according to CTCAE v5.0. A serious adverse event is one that results in death, is life-threatening, requires in-patient hospitalization or causes prolongation of existing hospitalization, results in persistent or significant disability/incapacity, may have caused a congenital anomaly/birth defect, or requires intervention to prevent permanent impairment or damage. Pregnancy during the reporting period will be classified as a serious adverse event.
- 2. Objective tumor response, per RECIST v1.1 (see Appendix C), in subjects with measurable disease. An objective tumor response can be observed at any time on study between 8 weeks after starting therapy (C3D1) through 18 months after starting therapy.
- 3. Progression-free survival (PFS), defined as the number of days to either progressive disease as defined per RECIST v1.1 or death.
- 4. Clinical benefit, defined as an objective tumor response or stable disease at 6 months, defined per RECIST v1.1 (see Appendix C).

#### 10.2.1 Measurement Methods

For those subjects with bone-only disease, RECIST v1.1 criteria will not be used to assess response. Subjects will stop study drug at when disease is deemed by the investigator to have progressed.

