# 3.1 Inclusion Criteria

	Prospective Participant Must MATCH ALL these Inclusion Criteria to be Eligible	Yes	No	Supporting Documentation *
1.	History of biopsy-proven ER-positive and/or PR-positive, HER2-negative breast cancer and radiographic evidence of metastatic disease, or locally recurrent unresectable disease. ER-positivity and PR-positivity are defined as ≥ 1% cells staining positive by immunohistochemistry. HER2-negativity is defined by IHC or FISH, per ASCO-CAP 2018 guidelines			
2.	Cancer subtype indicative of alterations to the fibroblast growth factor ligand or receptor (FGF/FGFR alteration): Predicted integrative (IntClust) subtype classification of IC2 or IC6 according classifier on targeted sequencing data from FoundationOne.			

IRB-53650 Version 11 Page 24 of 72 11 November 2021

	Prospective Participant Must MATCH ALL these Inclusion Criteria to be Eligible	Yes	No	Supporting Documentation *
3.	Evaluable or measurable disease.  Cohort 1 only: Evaluable or measurable disease, as defined by RECIST v1.1. Bone-only disease is acceptable.			
4.	≥ 18 years old			
5.	Eastern Cooperative Oncology Group (ECOG) performance status 0 to 2			
6.	Prior cancer therapy (except for endocrine therapy, denosumab, or bisphosphonates) must be discontinued for 2 weeks prior to initiation of study drugs. Recovery from adverse events of previous cancer therapies to baseline or Grade 1 except for alopecia or stable Grade 2 neuropathy. Radiotherapy must also be completed at least 2 weeks prior to initiation of study drugs			
7.	Absolute neutrophil count (ANC) ≥ 1,000/mm 			
8.	Platelets ≥ 75,000/mm 			
9.	Hemoglobin ≥ 9.0 g/dL			
10.	Total bilirubin ≤ 1.8 mg/dL (unless documented Gilbert's disease)			
11.	Aspartate aminotransferase (AST) and alanine aminotransferase (ALT) < 90 U/L			
12.	Estimated glomerular filtration rate (GFR) ≥ 45 mL/min			
13.	Phosphorus between 2.5 and 4.5 mg/dL, inclusive			
14.	Total corrected (for albumin) serum calcium between 8.5 and 10.5 mg/dL, inclusive			
15.	Amylase < 200 U/L			
16.	Lipase < 120 U/L			
17.	Ability to understand and the willingness to sign a written informed consent document			

Prospective Participant Must MATCH ALL these Inclusion Criteria to be Eligible	Yes	No	Supporting Documentation *

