# 9. STUDY CALENDAR

	Screening	On Treatment (1 Cycle = 28 days)						Post-Treatment			
2	(Within	Cycle 1			Cycle 2		Cycles ≥ 3	End of Treatment /	30-day		
	21 days of Cycle 1, Day 0)	Day 1 (± 3 days)	Day 4 (± 1 day)	Day 15 (± 3 days)	Day 1 (± 3 days)	Day 15 (± 3 days)	Day 1 (± 3 days)	withdrawal (0 to 14 days from decision to discontinue) 	Follow-up Safety Visit (+ 7 days)  F	Other Follow-up 	
Informed Consent 	Х										
Medical/Tumor History 	х										
Physical Examination (within 24 hours prior to start of each cycle) 	x	х		x	х		x	X	x	( X )	
ECOG Performance Status 	х	х		Х	Х		Х	Х	Х	( X )	
Safety Labs/Measurements	5										
Vital Signs (within 24 hours prior to start of each cycle) 	х	х		х	х		х	х	х	( X )	
Hematology (CBC, differential, platelets) 	х	х		х	х	Х	х	х		( X )	
Complete metabolic panel 7	Х	х	Х	Х	Х	Х	X	Х		(X)	
Amylase, lipase 	х	Х		Х	Х	Х	Х	х		( X )	
Calcium, magnesium, phosphorus 	х	х	х	х	х	Х	x	х		( X )	
Urinalysis 10	Х										
Pregnancy Test 11	х	Х						х			
Electrocardiogram 12	х				х		C4D1, C6D1 (± 7 days) then every 6 cycles (all ± 14 days)	х			
Transthoracic echocardiogram	х				х			х			
Ophthalmology evaluation 	х				X ± 7 da ys		C3D1, C4D1, C6D1 (± 7 days), then every 3 cycles (± 14 days)	х			

IRB-53650 Version 11 Page 52 of 72 11 November 2021

Hormone Receptor-positive, HER2-negative, FGFR-altered Advanced Breast Cancer

	Screening			On Tre	eatment (	Post-Treatment				
	(Within	Cycle 1		Сус	ele 2	Cycles ≥ 3	End of Treatment /	30-day		
Protocol Activity	21 days of Cycle 1, Day 0)	Day 1 (± 3 days)	Day 4 (± 1 day)	Day 15 (± 3 days)	Day 1 (± 3 days)	Day 15 (± 3 days)	Day 1 (± 3 days)	withdrawal (0 to 14 days from decision to discontinue) 	Follow-up Safety Visit (+ 7 days)  Fol	
Registration 	≤ 7 days bef Cycle 1, Day 1									
Treatment										
Infigratinib administration 			1 week off			3 weeks on / 1 week off 3 weeks on / 1 week off				
Cohort 1: Tamoxifen administration 			Continuous		Continuous		Continuous			
Tumor Assessment										
CT (chest, abdomen, pelvis) 	х						C3D1 (+7 days), then every 2 cycle (± 7 days)	( X )		
Plasma collection 		х		х				Х		
Research tumor biopsy 19	Х			х						
Tumor sequencing 	Х									

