### 10.2.2 Measurement Time Points

Antitumor activity will be assessed through radiological tumor assessments conducted at baseline, on treatment every 8 weeks (± 7 days), and whenever disease progression is suspected (eg, symptomatic deterioration). After 12 months of therapy, imaging can be spaced out to every 12 weeks (± 7 days) at the Investigator's discretion. Studies will be repeated at End of Treatment/Withdrawal only if not done in the previous 4 weeks. Confirmation of response (CR/PR) should be done at least 4 weeks after the initial response. Timing should follow calendar days (starting from C1D1) and should not be adjusted for delays in cycle starts.

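### PFS and clinical benefit are defined by RECIST alone, but bone-only subjects are eligible and are assessed outside RECIST, so their outcomes are undefined or miscounted

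*Combined protocol and SAP*

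**What the plan says.** - **Eligibility (3.1, criterion 3).** "Bone-only disease is acceptable". No cap or stratification is stated.
- **Assessment (10.2.1).** "For those subjects with bone-only disease, RECIST v1.1 criteria will not be used to assess response". The next sentence reads: "Subjects will stop study drug at when disease is deemed by the investigator to have progressed".
- **PFS (10.2, item 3).** "defined as the number of days to either progressive disease as defined per RECIST v1.1 or death". Section 10.3.2 repeats this and describes progressive disease as a 20% increase in the target-lesion sum and/or new lesions.
- **Clinical benefit (10.2, item 4).** "defined as an objective tumor response or stable disease at 6 months, defined per RECIST v1.1". Unlike objective response, it is not limited to subjects with measurable disease. Section 1.2 calls it a rate; 10.3.2 reports a number of subjects by final dose level.
- **Analysis set (12.7).** Everyone who received at least one dose of infigratinib is analysed for efficacy.
- **Presentation (12.6).** Kaplan-Meier plots of PFS overall and separately for IC2 and IC6. No censoring rule is given.
- **Appendix C.** Bone disease without a measurable soft-tissue component is non-measurable, and non-measurable disease is non-target. Progression can be declared on non-target disease or on a new lesion.

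**The concern.** Section 10.2.1 handles bone-only subjects outside RECIST, while the two endpoint definitions recognise nothing else. No text joins them: nothing says that investigator-judged progression is a PFS event, how these subjects are censored, or whether they belong in the clinical-benefit denominator.

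The two endpoints err in the favourable and the unfavourable direction respectively. If progressions are dropped, PFS looks too long. If subjects who are progression-free at 6 months cannot be classed as stable, clinical benefit looks too low. Both are stated secondary objectives and ClinicalTrials.gov outcomes. With at most 12 evaluable subjects, split further by dose level or integrative subtype, the handling of one or two subjects can change the reported result. Two analysts could follow the text in good faith and date, or censor, the same subject differently.

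**Working it through.** The plan states no PFS figure, event count or target rate, so there is nothing to reproduce. The check sets the definitions side by side and then sizes the consequence under stated assumptions.

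**Clinical benefit.** Take a bone-only subject with no measurable soft-tissue component and no progression at 6 months.
1. All disease is non-target, so there is no target-lesion status.
2. In the Appendix C table, the CR, PR and Stable rows each require a target status of CR, PR or SD.
3. The nearest row is target Indeterminate or Missing, non-target Non-PD, no new lesion. Its result is Indeterminate.
4. Indeterminate is neither a response nor stable disease, so the subject is not counted as clinical benefit under 10.2.
5. Section 12.7 keeps the subject in the analysis. With *k* bone-only subjects among 12, the highest attainable rate is (12 − *k*)/12. For an assumed *k* = 3 this is 9/12 = 75%, even if nobody progresses.

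**PFS: which progressions count?**

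| Source | Routes to an event for a bone-only subject |
|---|---|
| 10.2 with Appendix C | unequivocal non-target progression, new lesion, death |
| 10.3.2 | new lesion, death (its criteria list gives no non-target route) |
| 10.2.1 | investigator judgement stops drug; no link to PFS |

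Under the 10.3.2 text, worsening of existing bone lesions alone is not progression. Once drug stops on the investigator's judgement, later events may also be missed: 4.2 allows follow-up to end when another regimen starts, and the Study Calendar has no survival follow-up row.

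**PFS: size if every such progression is censored.**
- Assumed median: 5.5 months, borrowed from the dovitinib–fulvestrant trial described in 2.3.1; exponential, with the same hazard in all subjects.
- Bone-only share *b*: not in the documents; taken as 1 to 4 of 12.
- Censoring at progression leaves a pooled event hazard of (1 − *b*)λ, so the apparent median is 5.5/(1 − *b*).

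| Bone-only | 5.5/(1 − *b*) | Months | Typical Kaplan-Meier median, N = 12 |
|---|---|---|---|
| 0 of 12 | 5.5/1 | 5.5 | 4.9 |
| 1 of 12 | 5.5 × 12/11 | 6.0 | 5.5 |
| 2 of 12 | 5.5 × 12/10 | 6.6 | 6.3 |
| 3 of 12 | 5.5 × 12/9 | 7.3 | 7.2 |
| 4 of 12 | 5.5 × 12/8 | 8.25 | 8.1 |

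The last column is the middle value over 10,000 simulated trials of 12 subjects with a cut-off at 18 months. It starts at 4.9 rather than 5.5 because the Kaplan-Meier median is biased low in so small a sample; the relevant comparison is down the column.

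**PFS: size if bone-only subjects are instead followed to death only.** Assume a median survival of 36 months (2.1 gives approximately 3 years). Solving (1 − *b*)exp(−λt) + *b* exp(−μt) = 0.5 at *b* = 25% gives 7.7 months, close to the 7.3 months above.

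**The case against.** A reader might infer that bone-only progression can never be a PFS event and that PFS is therefore biased upward. The documents do not support that.

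- Section 10.2.1 sets RECIST aside for response; it does not expressly do so for progression.
- Appendix C gives two routes to progression without target lesions, and its table returns PD for any target status when either is met. Section 3.1 admits these subjects under RECIST-defined evaluable disease, and 4.2 lists RECIST progression as a reason to stop treatment with no bone-only exception.
- Death always counts.
- Censoring at investigator progression is an inference, since no rule is written. Section 12.6 lists a progression date for each subject, and 10.3.2 introduces PFS as being alive without return or relapse of tumour. Both are compatible with counting the investigator's call.
- The bone-only share is unknown and may be zero.
- Chance dwarfs the shift: in simulated trials of 12, the central 95% range of the median is about 1.9 to 10.2 months with no bone-only subjects and about 2.7 to 15.1 with three censored.

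These points stand, and they reduce the PFS finding from an established bias to an undefined event with a possible bias. They do not close the gap: the PD wording in 10.3.2 omits the non-target route, and nothing says that Appendix C, rather than the investigator's judgement, sets the PFS date.

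On clinical benefit the defence is weaker. Stable disease in 10.3.2 is a residual category that might be stretched to cover these subjects. However, the criteria it falls back from are largely worded in terms of target lesions, and 10.2 refers the reader to Appendix C, where the result is Indeterminate.

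**Conclusion.** The concern holds for both endpoints, with different force.

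**Clinical benefit** is wrong as written. A bone-only subject who is progression-free at 6 months cannot be counted, so the rate is understated if such subjects stay in the denominator. The 75% ceiling rests on an assumed 3 of 12.

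**PFS** is underspecified. Investigator-judged progressions that stop treatment can be lost. If all are lost, an assumed 5.5-month median reads as 6.0 to 8.25 months for 1 to 4 of 12 bone-only. If Appendix C progression is applied to these subjects, only judgements falling short of RECIST PD are lost, and the bias is smaller and may be zero. With no bone-only subjects it is zero.

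The impact is limited to secondary endpoints that are analysed descriptively, with no hypothesis test. The DLT endpoint and the dose decision are unaffected. The change should still be made, because settling the rule before analysis avoids a post hoc choice in a very small data set.

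**What to change.** **PFS (10.2 and 10.3.2).** Define the event as the first of: RECIST v1.1 progression, stated to include unequivocal non-target progression and new lesions; for bone-only subjects, investigator-determined progression as in 10.2.1; or death. State the censoring rule, including for subjects who start another regimen without an event.

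**Clinical benefit (10.2 and 10.3.2).** Choose one and state it: (a) count bone-only subjects who have not progressed at 6 months (Non-CR/Non-PD in Appendix C terms); or (b) restrict the denominator to subjects with RECIST-measurable disease. Option (a) keeps the 12.7 population intact. Option (b) is simpler but shrinks an already small denominator.

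**Cost.** Two definitions are reworded, with matching text for the registry outcomes. No scans, visits, subjects or treatment rules change. PFS may look slightly less favourable, because progressions that might have been censored become events.

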### 10.2.2 Measurement Time Points

Antitumor activity will be assessed through radiological tumor assessments conducted at baseline, on treatment every 8 weeks (± 7 days), and whenever disease progression is suspected (eg, symptomatic deterioration). After 12 months of therapy, imaging can be spaced out to every 12 weeks (± 7 days) at the Investigator's discretion. Studies will be repeated at End of Treatment/Withdrawal only if not done in the previous 4 weeks. Confirmation of response (CR/PR) should be done at least 4 weeks after the initial response. Timing should follow calendar days (starting from C1D1) and should not be adjusted for delays in cycle starts.

### 10.3 Outcomes for ClinicalTrials.gov

The outcomes for ClinicalTrials.gov represent the study objectives.

### 10.3.1 Primary Outcome

**Primary Outcome Title**: Dose-limiting Toxicity (DLT)

**Primary Outcome Measure Description**: The primary outcome for this study is dose-limiting toxicities (DLTs) during the first 2 cycles of therapy at a specific dose. All grades per the Common Terminology Criteria for Adverse Events (CTCAE). DLT is defined as a related and clinically-significant adverse event (AE), including missed doses due to a related AE. Due to limited number of characters that can present in this field, it is not possible to consistently provide additional details across all sub-elements of this outcome. See protocol. The outcome is expressed as the number of DLT events by the assigned infigratinib dose level, a number without dispersion.

Time Frame: 8 weeks.

# 10.3.2 Secondary Outcomes

1. **Outcome Title**: Treatment-emergent Adverse Events (TEAE)

**Outcome Measure Description**: Treatment-emergent adverse events (TEAEs) are defined as adverse events of any grade with initial onset or increasing in severity after the first dose of study treatment until 30 days after last dose of study drug. Pregnancy during the reporting period will be classified as a serious adverse event. The outcome will be expressed as the number of events by the infigratinib dose level at the time of the event, stratified by relatedness and Common Terminology Criteria for Adverse Events (CTCAE) grade. The result is a number without dispersion.

**Time Frame**: 2 years

2. Outcome Title: Objective Tumor Response

**Outcome Measure Description**: Objective tumor response will be assessed as achieving a Response Evaluation Criteria in Solid Tumors (RECIST) v1.1 Complete Response (CR) or a Partial Response (PR). The outcome will be reported as the number of subjects by each participant's final infigratinib dose level that achieve an overall response (OR) to treatment, ie, CR or PR, within 18 months of starting treatment. The outcome will be reported as a number without dispersion. RECIST criteria are:

- CR = Disappearance of all target lesions
- PR =  $\geq$  30% decrease in the sum of the longest diameter of target lesions
- Overall Response (OR) = CR + PR
- Progressive disease (PD) = 20% increase in the sum of the longest diameter of target lesions, and/or the appearance of one or more new lesion(s)
- Stable disease (SD) = Small changes that do not meet any of the above criteria

**Time Frame**: up to 18 months

3. **Outcome Title**: Progression-free Survival (PFS)

**Outcome Measure Description**: Progression-free survival (PFS) means the subject is alive without return or relapse of the tumor. The outcome is defined as the number of

days to either progressive disease as defined per RECIST v1.1 or death, by each participant's final infigratinib dose level, and reported as the median PFS with full range. RECIST criteria are:

- CR = Disappearance of all target lesions
- PR = ≥ 30% decrease in the sum of the longest diameter of target lesions
- Overall Response (OR) = CR + PR
- Progressive disease (PD) = 20% increase in the sum of the longest diameter of target lesions, and/or the appearance of one or more new lesion(s)
- Stable disease (SD) = Small changes that do not meet any of the above criteria

Time Frame: Up to 2 years.

4. **Outcome Title**: Clinical Benefit

**Outcome Measure Description**: Clinical benefit will be assessed as achieving a Response Evaluation Criteria in Solid Tumors (RECIST) v1.1 Complete Response (CR); Partial Response (PR); or Stable Disease (SD). The outcome will be reported as the number of subjects by each participant's final infigratinib dose level that achieve a CR; PR; or SD, within 6 months of starting treatment. The outcome will be reported by treatment and dose level as a number without dispersion. RECIST criteria are:

- CR = Disappearance of all target lesions
- PR = ≥ 30% decrease in the sum of the longest diameter of target lesions
- SD = Small changes that do not meet any of the above criteria
- Progressive disease (PD) = 20% increase in the sum of the longest diameter of target lesions, and/or the appearance of one or more new lesion(s)
- SD = Small changes that do not meet any of the above criteria

Time Frame: up to 6 months

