# 12.4 Primary Safety Analysis

Cohort 1 (infigratinib plus tamoxifen) will follow the 3+3 design evaluating 3 infigratinib doses levels, starting at 100 mg infigratinib 3 weeks on/1 week off) and moving to, if needed, 75 mg or 125 mg infigratinib 3 weeks on/1 week off. Given the nature of this cohort to be a safety run-in and the limited number of available subjects for this population, intra-subject dose-escalation will be allowed. The risk with intra-subject dose-escalation is that a dose may be declared overly toxic when the toxicities should be attributed to the number of cycles rather than the dose, but it is believed this is a conservative approach focused on subject safety.

Initially, 3 subjects will be treated at 100 mg for 2 cycles. If there are no DLTs observed in a subject at 100 mg after 2 cycles, the subject will escalate to 125 mg for 2 additional cycles. If 1 DLT is observed at 100 mg, an additional 3 subjects will be treated at 100 mg. If 2 or more DLTs are observed at 100 mg, an additional 3 subjects will be treated at 75 mg. If 1 DLT is observed at 75 mg, an additional 3 subjects will be treated at 75 mg. If no DLTs are observed in the first 3 subjects at 100 mg, but 1 DLT is observed at 125 mg, an additional 3 subjects will be treated at 125 mg, an additional 3 subjects will be treated at 125 mg. If 2 or more DLTs are observed at 125 mg, Cohort 1 will close. If a dose achieves no DLTs in 3 subjects after 2 cycles or 1 DLT in 6 subjects after 2 cycles, that dose will be declared safe for use in the main phase 2 trial.

If a subject withdraws prior to the completion of the first 2 cycles of therapy without having experienced a DLT, an additional subject will be enrolled at that dose level.

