# 12.5 Secondary Safety Analysis

The secondary safety analysis relates to the incidence of treatment-emergent adverse events (TEAEs). TEAEs are those with initial onset or increasing in severity after the first dose of study treatment. TEAEs will be graded by the investigator according to the Common Terminology Criteria for Adverse Events (CTCAE) version 5.0 and coded using the Medical Dictionary for Regulatory Activities (MedDRA). The number and percentage of subjects who experienced any AE, serious AE (SAE), treatment-related AE, and treatment-related SAE will be summarized according to worst toxicity grades. The summaries will present AEs both on the entire study period and by cycle (Cycle 1 and Cycles beyond 1) in Cohort 1.

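### No planned output gives TEAE incidence by infigratinib dose: the by-dose outcome is an event count with no denominator, and the subject-level table is not split by dose

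*Combined protocol and SAP*

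**What the plan says.** The secondary objective (Section 1.2) and the endpoint (Section 10.2) are worded as incidence of TEAEs. Two places turn this into output.

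- Section 10.3.2, by dose: "The outcome will be expressed as the number of events by the infigratinib dose level at the time of the event", stratified by relatedness and grade. It adds: "The result is a number without dispersion". No number of subjects at risk and no exposure time is requested. Section 10.3 says that these outcomes represent the study objectives.
- Section 12.5, by subject: "The number and percentage of subjects who experienced any AE, serious AE (SAE), treatment-related AE, and treatment-related SAE will be summarized" by worst grade. The breakdown is "both on the entire study period and by cycle (Cycle 1 and Cycles beyond 1) in Cohort 1". Dose is not a breakdown variable.

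Nothing else fills the gap. The laboratory summaries that follow Section 12.5 use the same cycle split, Section 12.7 defines one pooled population, and the dose listing in Section 12.6 belongs to the efficacy data.

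Exposure by dose is unequal by design. Section 12.4 states: "Initially, 3 subjects will be treated at 100 mg for 2 cycles". Subjects without a DLT then move to 125 mg. Section 12.4 describes two further cycles at 125 mg. Section 10.1 has the increase begin at Cycle 3 and gives no end. Section 4 lets treatment run to 18 months. The dose after Cycle 4 is not stated.

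**The concern.** The two summaries do not complement each other. One is by dose but has no denominator; the other has a denominator but is not by dose. The Cycle 1 versus later split does not help either: for an escalated subject it cuts between two cycles at the same dose and then merges the second of them with all cycles at the higher dose. It matches neither a dose period nor the two-cycle DLT window.

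A reader of the by-dose table will nevertheless compare the dose columns. Differences between them can come from a true dose effect, from time spent at each dose, or from the fact that 100 mg comes first and 125 mg second. A count cannot separate these. With 3 to 12 evaluable subjects, one person with several events can also carry a column. At stake is the by-dose tolerability description that accompanies the recommended dose.

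**Working it through.** **Plan's own figure.** The documents give no TEAE count, rate or exposure by dose. The only design number nearby is the sample size in the Synopsis, 3 to 12 evaluable. Following Section 12.4: the minimum is 3 (0/3 at 100 mg, the same three escalate, 0/3 at 125 mg), and the maximum is 6 at 100 mg plus 6 at 75 mg = 12. Both reproduce. This is a consistency check only.

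**Inputs.**
- Cycle of 28 days, maximum 18 months (Section 4): 18 × 365.25/12 ÷ 28 = 19.57 cycles.
- Two cycles at 100 mg before escalation (Sections 10.1 and 12.4).
- Time on treatment: assumed exponential. Medians of 5.5 and 10.9 months are borrowed from the PFS figures of the dovitinib plus fulvestrant trial described in Section 2.3.1; 3 months is added as a low case.
- p, the chance of not escalating because of a DLT at 100 mg: 1/6 from the single-agent data in Section 2.2.9, range 0 to 1/3. This too is an assumption.

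**Formulas.** With L = ln 2 ÷ (median in cycles), expected cycles per subject are:
- at 100 mg: (1 − exp(−2L))/L
- at 125 mg if continued: (1 − p)(exp(−2L) − exp(−19.57L))/L
- at 125 mg in Cycles 3 and 4 only: (1 − p)(exp(−2L) − exp(−4L))/L

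If the true event rate per cycle is the same at both doses, the count ratio equals the exposure ratio. In the last case, treatment after Cycle 4 is counted at neither dose.

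**Worked case.** A median of 5.5 months is 5.98 cycles, so L = 0.1159. At 100 mg: (1 − 0.7931)/0.1159 = 1.79. At 125 mg, continued, p = 0: (0.7931 − 0.1034)/0.1159 = 5.95. The ratio is 3.33.

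| Median (months) | p | Cycles at 100 mg | Cycles at 125 mg, continued | Ratio | Cycles at 125 mg, Cycles 3–4 only | Ratio |
|---|---|---|---|---|---|---|
| 3 | 0 | 1.63 | 3.00 | 1.84 | 1.07 | 0.65 |
| 3 | 1/3 | 1.63 | 2.00 | 1.23 | 0.71 | 0.44 |
| 5.5 | 0 | 1.79 | 5.95 | 3.33 | 1.42 | 0.79 |
| 5.5 | 1/6 | 1.79 | 4.96 | 2.78 | 1.18 | 0.66 |
| 10.9 | 0 | 1.89 | 9.77 | 5.17 | 1.68 | 0.89 |
| 10.9 | 1/6 | 1.89 | 8.14 | 4.31 | 1.40 | 0.74 |

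(Ratios use unrounded cycles.) The ceiling is one escalated subject who stays on 125 mg to 18 months: (19.57 − 2)/2 = 8.8.

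**In counts.** Six subjects, one TEAE per cycle at either dose, median 5.5 months, p = 1/6, 125 mg continued: about 11 events at 100 mg and 30 at 125 mg, with no dose effect.

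**Early clustering.** Let the rate in Cycles 1–2 be k times the later rate, with no dose effect and 125 mg continued. The count ratio is then divided by k:

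| k | 5.5 months, p = 1/6 | 5.5 months, p = 0 | 10.9 months, p = 0 |
|---|---|---|---|
| 1 | 2.78 | 3.33 | 5.17 |
| 2 | 1.39 | 1.67 | 2.59 |
| 3 | 0.93 | 1.11 | 1.72 |
| 4 | 0.69 | 0.83 | 1.29 |

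**With a denominator.** Events per subject-cycle give a 125:100 ratio of 1.0 in every equal-rate case above. They do not remove the cycle effect: with k = 3 and no dose effect, the rate ratio for escalated subjects would be 1/3.

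**The case against.** A reader might infer that 125 mg will look more toxic simply because subjects stay on it longer. The documents do not support that, for three reasons. First, it needs every cycle after the second to be at 125 mg, and Sections 10.1 and 12.4 do not settle this; on the reading of two further cycles only, the ratio falls below 1. Second, it needs a constant event rate, whereas "A TEAE is defined as an adverse event with initial onset or increasing in severity after the first dose of study treatment" means that ongoing events are not recounted. Early onsets fall on 100 mg: Section 2.2.9 reports a median of 22 days to drug interruption under continuous dosing, linked to hyperphosphatemia. Third, DLTs, dose reductions (Section 6) and progression shorten time at 125 mg, and subjects enrolled directly at 125 mg would have their first cycles there.

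A reader might also infer that the dose choice is biased. It is not. The rule in Section 12.4 counts DLTs over two cycles at each dose among 3 or 6 subjects. Section 12.4 itself acknowledges that toxicity after escalation may reflect cycle number.

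Finally, it can be said that the analyses are descriptive (Section 12.1), that no between-dose TEAE test is planned, that Section 10.3 is registry text, and that Section 12.5 already delivers overall incidence. All of that stands and limits the weight of the point. It does not supply incidence by dose, and a dose breakdown is what Section 10.3.2 sets out to report.

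**Conclusion.** The gap is real, and it is confined to secondary safety reporting. No planned output gives TEAE incidence by dose, and the by-dose counts mix dose with exposure time and cycle order. Under equal rates the 125:100 count ratio could lie anywhere from 0.44 to 8.8, depending on how long subjects stay on 125 mg. The upper end is a single subject treated for the full 18 months; averaged over the assumed treatment durations, the continued-125 mg range is 1.2 to 5.2. Early clustering widens the uncertainty in the downward direction. A measure that can move this far in either direction with no dose effect does not describe tolerability by dose.

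The figures rest on assumed exponential treatment times, borrowed medians and an assumed escalation probability, and they ignore dose reductions and subjects who start at 125 mg. The absence of a denominator does not depend on any of these. The change is worth making because it is nearly free, not because the trial's main conclusion is at risk.

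**What to change.** In Sections 10.3.2 and 12.5:

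1. Report, by dose at onset, the number and percentage of subjects with at least one TEAE (by worst grade) among subjects exposed to that dose.
2. Alongside, give subject-cycles at that dose and events per subject-cycle. The event count can stay as the numerator.
3. Replace the split at Cycle 1 with the first two cycles at each dose against later cycles.
4. Show escalated subjects separately from those who started at that dose, and state that for escalated subjects dose and cycle order remain confounded. The new split still compares Cycles 1–2 with Cycles 3–4 for them.

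Sections 10.1 and 12.4 must also be reconciled on the dose after Cycle 4, since exposure by dose cannot be defined until they agree.

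The cost is programming and a short text change. AE start and end dates are on the CRF (Section 7.3) and drug accountability is recorded at each visit (Section 5.4), so dose at onset and subject-cycles can be derived. No change to visits or sample size is needed.
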